5.6 OTHER ASSESSMENTS

Not applicable.

5.7 APPROPRIATENESS OF MEASUREMENTS

All measurements conducted in the trial are using standard methods.

6. INVESTIGATIONAL PLAN

6.1 VISIT SCHEDULE

Informed consent of all study patients will be obtained in compliance with ICH and GCP guidelines and the principles stipulated in the Declaration of Helsinki prior to any study related procedures, including any washout of restricted medications (refer to [table 4.2.2.1:1](#)).

The study will consist of a screening period up to 28 days, a randomised treatment period of 24 weeks and a follow up period lasting a minimum of four weeks (28 days).

All patients are to adhere to the visit schedule as outlined in the [flow chart](#). Some flexibility is allowed in scheduling the visits according to the visit time windows as specified. The trial medication kits contain sufficient medication to allow for these time windows. All deviations from the planned visit schedule will be documented. If any visit is to be re-scheduled, subsequent visits should follow the original visit date schedule (calculated from visit 2). No protocol waivers will be given (e.g. sponsor will not grant permission to include a known ineligible patient).

6.2 DETAILS OF TRIAL PROCEDURES AT SELECTED VISITS

6.2.1 Screening and run-in period(s)

Screening Period

No study related procedures will be performed until the patient has signed informed consent. The study will be explained to patients and those who meet entry criteria ([section 3.3](#)) will be invited to participate.

Please refer to the flow chart for complete procedures at visit 1.

An echocardiogram will be performed with site equipment at visit 1 to evaluate cardiac function and assess exclusion criteria 10, 11 and 12 ([section 3.3.3](#)). In addition, this test will be used for the stratification of patients during randomization (as described in [section 7.6](#)). The following questions will be captured in the eCRF based on the investigator's judgement:

- Presence of right ventricular systolic dysfunction (yes/no)
- Presence of right ventricular hypertrophy (yes/no)
- Presence of right ventricular dilatation (yes/no)
- Presence of paradoxical septum motion (yes/no)
- Presence of right atrium enlargement (yes/no)

Clinically relevant findings will be recorded as baseline conditions.

Patients who have a laboratory test, blood pressure or lung function test value outside the range specified by the exclusion criteria and thought to be a measurement error or the result of a temporary and reversible medical condition may have the test repeated once to determine

eligibility; however, the result must be available prior to visit 2. The period between visit 1 and visit 2 should last a maximum of 28 days. If visit 2 could not be performed within this timeframe the patient will be considered as screen failed.

All patients who have signed consent must be entered in the enrolment log and documented in the eCRF. Patients found to be ineligible at or prior to visit 2 and do not initiate treatment will be considered a screen failure.

6.2.2 Treatment period(s)

If the patient has been determined eligible by the investigator to enter the trial (refer to [section 3.3](#)), the investigator will assign medication numbers to the patient through the IRT system at visit 2. First dose of trial drugs will be administered at visit 2 in the clinic (day 1).

Additional clinic visits will be scheduled after 4, 8, 12, 18 and 24 weeks of treatment (visits 3-7). For detailed description of the trial procedures at each visit and dispensing schedule, please refer to the [flow chart](#).

Dose Adjustment Visit

The dose of nintedanib can be reduced and increased as described in [section 4.2.1](#). In this case, the patient will be required to return to the clinic for an unscheduled visit where new medication will be assigned via the IRT system. Please refer to the flow chart for complete procedures in this visit.

6.2.3 Follow Up Period and Trial Completion

A follow-up (FUP) visit should be planned for 28 days after last trial drug administration. For detailed description of the trial procedures at the FUP visit, please refer to the flow chart.

Trial completion

The trial completion eCRF page has to be filled-in when the patient has terminated the trial. The end of the trial is:

- At the end of the follow-up visit for patients who have completed the trial on treatment as planned;
- After the early end of treatment (EOT) and follow-up visits, if a patient did not agree to come to the remaining planned study visits;
- At the end of visit 7 for patients who discontinued drug early but agreed to come to the remaining planned study visits.

Patients who prematurely discontinued trial medication

Patients who prematurely discontinue all study drugs (refer to [section 3.3.4](#)) before the planned end of treatment at visit 7, should come to the clinic as soon as possible after last drug intake for an early EOT visit. Reason for discontinuation must be documented in the eCRF. For detailed description of the trial procedures at this visit, please refer to the [flow chart](#).

In addition patients will be invited to attend all planned visits despite not being under treatment anymore and perform all study procedures except the laboratory tests (optional), biomarker sampling, pharmacokinetic sampling and the ECG. If patients don't accept to attend all remaining study visits, they will be contacted for vital status collection at week 24.

The need for coming to future visits in case of premature discontinuation of trial medication will be explained to patients prior to their participation in the trial.

Vital status information

In case of early discontinuation of all study drugs, if the patient does not agree to come to future visits as planned, every attempt will be made to get information on vital status at week 24 after his/her randomization.

Patients will be asked to agree to be contacted by the site personnel, which could be by telephone calls, to allow collection of this information.

If death occurs, the investigator will review the circumstances, including the relevant medical records to ascertain the most likely primary and secondary causes of death.

Collection of vital status will be performed in accordance with national ethical and regulatory guidelines. The need for vital status information will be explained to patients prior to their participation in the trial.

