 13. Patients who complete an early End of Treatment visit and don't accept to attend all remaining planned visits will be contacted for vital status collection at week 24. This can be done by phone.
 14. Visit 2 is defined as baseline assessment if the respective parameter is planned to be collected at that visit. Otherwise, visit 1 will serve as baseline assessment.
 15. Visit 7 is the End of Treatment (EOT) visit for patients who complete the treatment period as planned.
 16. In case of dose change of nintedanib (reduction or re-escalation), dose adjustment visit must be conducted to allow dispensing of new medication kit.
 17. Early end of treatment visit to be completed for all patients who withdraw or discontinue all study drugs prematurely. These patients will be invited to attend all remaining visits as planned until week 24 (Visit 7). The following procedures are no longer required in the visits to be conducted after the early EOT visit: laboratory tests, biomarker sampling, pharmacokinetic sampling and ECG.
 18. A follow up visit needs to be completed 28 days (+7 days) after the last drug administration for all patients. Patients who prematurely discontinue all study drugs but accept to conduct all remaining study visits as planned and the remaining duration in the trial is longer than 28 days after the last drug administration are exempted from this visit.

TABLE OF CONTENTS

TITLE PAGE	1
CLINICAL TRIAL PROTOCOL SYNOPSIS	2
FLOW CHART	5
TABLE OF CONTENTS	7
ABBREVIATIONS	11
1. INTRODUCTION.....	13
1.1 MEDICAL BACKGROUND	13
1.2 DRUG PROFILE	14
1.2.1 Nintedanib.....	14
1.2.2 Sildenafil	16
2. RATIONALE, OBJECTIVES, AND BENEFIT - RISK ASSESSMENT	18
2.1 RATIONALE FOR PERFORMING THE TRIAL	18
2.2 TRIAL OBJECTIVES.....	19
2.3 BENEFIT - RISK ASSESSMENT.....	19
3. DESCRIPTION OF DESIGN AND TRIAL POPULATION.....	21
3.1 OVERALL TRIAL DESIGN AND PLAN	21
3.1.1 Administrative structure of the trial	21
3.2 DISCUSSION OF TRIAL DESIGN, INCLUDING THE CHOICE OF CONTROL GROUP(S)	23
3.3 SELECTION OF TRIAL POPULATION	23
3.3.1 Main diagnosis for trial entry	23
3.3.2 Inclusion criteria	24
3.3.3 Exclusion criteria	24
3.3.4 Removal of patients from therapy or assessments.....	27
3.3.4.1 Removal of individual patients	27
3.3.4.2 Discontinuation of the trial by the sponsor	28
4. TREATMENTS.....	29
4.1 TREATMENTS TO BE ADMINISTERED.....	29
4.1.1 Identity of BI investigational product and comparator product.....	29
4.1.2 Method of assigning patients to treatment groups.....	29

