5.3.7 Adverse event collection and reporting

AE Collection

The investigator shall maintain and keep detailed records of all AEs in the patient files.

The following must be collected and documented on the appropriate eCRF by the Investigator:

- From signing the informed consent onwards through the Residual Effect Period (REP), until individual patient's end of trial: all AEs (serious and non-serious) and all AESIs. However, if an individual patient discontinues trial medication prematurely but stays in the trial (i.e. if further visits incl. telephone visits, or vital status assessments are planned) from then on and until the individual patient's end of the trial the Investigator must report related SAEs and related AESIs.
- After the individual patient's end of trial: the investigator does not need to actively monitor the patient for AEs but should only report relevant SAEs and relevant AESIs of which the investigator may become aware of.

[figure not shown]

Figure 5.3.7:1 AE Collection

The Residual Effect Period (REP) is defined as 28 days after the last trial medication administration. All AEs which occurred through the treatment phase and throughout the REP will be considered as on treatment please see [section 7.3.4](#). Events which occurred after the REP will be considered as post treatment events.

AE reporting to sponsor and timelines

The Investigator must report SAEs, AESIs, and non-serious AEs which are relevant for the reported SAE or AESI, on the BI SAE form via fax immediately (within 24 hours) to the sponsor's unique entry point (country specific contact details will be provided in the ISF).

The same timeline applies if follow-up information becomes available. In specific occasions the Investigator could inform the sponsor upfront via telephone. This does not replace the requirement to complete and fax the BI SAE form.

With receipt of any further information to these events, a follow-up SAE form has to be provided. For follow-up information the same rules and timeline apply as for initial information.

For Japan only: All SAEs must be reported immediately to the head of the trial site. With receipt of any further information to these events, a follow-up SAE form has to be provided. For follow-up information the same rules and timeline apply as for initial information.

Information required

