7.3.4 Safety analyses

Analysis of key safety endpoints is described in [sections 7.3.2](#) and [7.3.3](#).

Adverse events will be coded using the Medical Dictionary for Regulatory Activities (MedDRA) coding dictionary. Standard BI summary tables and listings will be produced. All adverse events with an onset between start of treatment and end of the residual effect period (REP), a period of 28 days after the last dose of trial medication, will be assigned to the treatment period for evaluation.

All treated patients will be included in the safety analysis. In general, safety analyses will be descriptive in nature and will be based on BI standards. No hypothesis testing is planned.

Statistical analysis and reporting of adverse events will concentrate on treatment-emergent adverse events. To this end, all adverse events occurring between start of treatment and end of the residual effect period will be considered 'treatment-emergent'. The residual effect period is defined as 28 days. Adverse events that start before first drug intake and deteriorate under treatment will also be considered as 'treatment-emergent'.

Frequency, severity, and causal relationship of adverse events will be tabulated by system organ class and preferred term after coding according to the current version of the Medical Dictionary for Drug Regulatory Activities (MedDRA).

Laboratory data will be analysed both quantitatively as well as qualitatively. The latter will be done via comparison of laboratory data to their reference ranges. Values outside the reference range, as well as values defined as clinically relevant, will be highlighted in the listings. Treatment groups will be compared descriptively with regard to distribution parameters as well as with regard to frequency and percentage of patients with abnormal values or clinically relevant abnormal values.

Vital signs, physical examinations, or other safety-relevant data observed at screening, baseline, during the course of the trial and at the end-of-trial evaluation will be assessed with regard to possible changes compared to findings before start of treatment.

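### Protocol 6.2.3 closes patients who stop drug late but keep attending at visit 7, while flow chart footnote 18 still requires their 28-day follow-up visit, so active AE monitoring may lapse inside the residual effect period

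*Protocol*

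**What the plan says.** **End of trial.** Protocol 6.2.3 lists three cases. Completers end at the follow-up visit. Early discontinuers who decline further visits end after the early end-of-treatment and follow-up visits. The third case is "At the end of visit 7 for patients who discontinued drug early but agreed to come to the remaining planned study visits". It has no condition on the date of last dose. The same section opens with a general rule: "A follow-up (FUP) visit should be planned for 28 days after last trial drug administration".

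**Follow-up visit.** Flow chart footnote 18 says "A follow up visit needs to be completed 28 days (+7 days) after the last drug administration for all patients". Its exemption covers patients who stop all study drugs early and keep attending, but only where "the remaining duration in the trial is longer than 28 days after the last drug administration are exempted from this visit".

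**AE collection.** Protocol 5.3.7 states that "The Residual Effect Period (REP) is defined as 28 days after the last trial medication administration". Full AE collection runs "From signing the informed consent onwards through the Residual Effect Period (REP), until individual patient's end of trial". After that point "the investigator does not need to actively monitor the patient for AEs", although relevant SAEs and AESIs that come to the investigator's attention should still be reported. The section also says that once a patient stops medication early but stays in the trial, related SAEs and related AESIs must be reported until the end of trial.

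**Analysis.** Protocol 7.3.4 states that events with onset up to the end of the residual effect period, "a period of 28 days after the last dose of trial medication, will be assigned to the treatment period for evaluation". SAP 6.1 and 7.8.1 use the same 28-day limit.

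**The concern.** A site cannot both complete a patient at visit 7 and hold a required visit for the same patient up to 27 days later, plus the window. The third case in 6.2.3 is the odd one out. Completers and patients who refuse further visits are both carried to the follow-up visit. Only the late discontinuer who agrees to stay can be closed before 28 days after the last dose, so cooperation shortens post-dose observation. Nothing in the documents suggests that this was intended.

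What is at stake is the completeness of safety data. If a site follows 6.2.3 and fills in the trial completion page at visit 7, 5.3.7 releases it from active monitoring while part of the residual effect period is still to run. SAP 7.8.1 counts patients with events, so a patient whose only event of a given type falls in that stretch and is not collected appears event-free. The primary objective in protocol 2.2 includes safety of the combination, and protocol 2.3 says it is unknown whether co-administration brings additional side effects. The follow-up period therefore matters.

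**Working it through.** The plan states no figure to reproduce. The check is day arithmetic.

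**Inputs**
- Planned day of visit 7: V = 169, window ±7 days, so 162 to 176 (protocol flow chart).
- Residual effect period: 28 days after last dose (protocol 5.3.7 and 7.3.4).
- Follow-up visit: 28 to 35 days after last dose (footnote 18).
- Last dose on day L, for a patient who attends the remaining visits.

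**Formulas**
- Follow-up visit still required if V − L ≤ 28. I read the remaining duration in footnote 18 as the time to visit 7.
- Residual-effect days after the 6.2.3 end of trial = max(0, L + 28 − V).

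**Results with V = 169**

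| Last dose L | V − L | Footnote 18 | Period ends, L + 28 | Days after visit 7 | Follow-up visit due |
|---|---|---|---|---|---|
| 140 | 29 | exempt | 168 | 0 | none |
| 141 | 28 | required | 169 | 0 | 169–176 |
| 148 | 21 | required | 176 | 7 | 176–183 |
| 155 | 14 | required | 183 | 14 | 183–190 |
| 162 | 7 | required | 190 | 21 | 190–197 |
| 168 | 1 | required | 196 | 27 | 196–203 |

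The two rules conflict for last doses on days 141 to 168. At exactly 28 days (day 141) they conflict, but no residual-effect day is left uncovered. If visit 7 is held on day 162 or 176, the range moves to 134–161 or 148–175, and the uncovered time is still 0 to 27 days. If stopping were even over the 28 days (an assumption), the mean would be (0 + 27)/2 = 13.5 days.

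**How many patients.** The documents give no discontinuation rate. As an illustration only, assume that 20–30% of 250 patients stop all drugs early, evenly over 168 days. Then 50 to 75 patients × 28/168 = 8.3 to 12.5 stop in this window. Those who decline further visits must be subtracted, because the second case in 6.2.3 already carries them to the follow-up visit. So even under these assumptions the figure is a ceiling.

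**Secondary SAE endpoint.** It runs from baseline to week 24 (protocol 5.1.2), which is day 169. With visit 7 on or after day 169, none of the uncovered days falls before week 24. With visit 7 at its earliest, at most 169 − 162 = 7 days do.

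**The case against.** The strongest reply is that other text already requires the visit. The opening sentence of 6.2.3 plans it, footnote 18 gives the specific rule, and protocol 6.1 tells all patients to follow the flow chart. A site that skipped the visit would breach the schedule. This shows that the visit was intended, but it does not remove the rule that says the patient is finished. The statement in 5.3.7 that collection runs through the residual effect period does not settle it either, because the same clause ends at the patient's end of trial.

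Three further objections stand and limit the point.

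- A reader might infer that the residual effect period itself is cut short. It is not. It is 28 days throughout, and SAP 6.1 starts the post-study period at the latest of several dates, one of which is last intake plus 29 days. Completion at visit 7 therefore cannot truncate the period in the analysis. Only collection within it can lapse.
- A reader might infer a biased comparison between arms. That would need late discontinuation, or the events missed after it, to differ by arm, and the documents give no evidence on this. Nor do they support a claim that patients who stop late mostly do so because they are deteriorating. Apart from the secondary SAE endpoint, the AE analyses are descriptive.
- The 5.3.7 sentence on related SAEs and related AESIs can be read as narrowing collection in these patients from the day they stop drug. If so, not all of the missing information comes from 6.2.3, and correcting 6.2.3 alone would not secure full AE collection. It is a separate tension about which events are reported. It does not decide when observation ends.

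Figure 5.3.7:1, on AE collection, is not shown in the text available and might clarify the intention.

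**Conclusion.** The point holds as an internal inconsistency. For patients who stop all drugs 28 days or less before visit 7 and attend the remaining visits, 6.2.3 and footnote 18 give incompatible ends of observation. Under 6.2.3 read with 5.3.7, active AE monitoring may lapse for the last 0 to 27 days of a 28-day period that protocol 7.3.4 and SAP 6.1 and 7.8.1 still treat as on-treatment.

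The likely effect is some under-counting in the descriptive treatment-emergent AE and SAE tables. It arises only where sites let the end-of-trial wording override the flow chart. The number of patients is small and cannot be derived from the documents. The secondary SAE endpoint is largely untouched, and a between-arm bias is conditional, not shown. The day ranges follow from the documents. The mean of 13.5 days and the patient count rest on the assumptions stated with them.

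**What to change.** Reword the third end-of-trial case in protocol 6.2.3: for patients who stop drug early and attend the remaining visits, the trial ends at visit 7 or at the follow-up visit that footnote 18 requires, whichever is later. That visit is due 28 to 35 days after the last dose, so the residual-effect days falling after the end of trial drop from 0–27 to 0. The cost is one sentence, since footnote 18 already plans the visit and no procedure is added.

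This closes the timing gap only. For full coverage of the period, also reconcile two statements in 5.3.7: that all AEs are collected through the residual effect period, and that only related SAEs and related AESIs must be reported once a patient stops early but stays in the trial. One way is to state that the narrower rule begins after the residual effect period. This costs another sentence and some extra AE recording for early discontinuers.

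If the protocol can no longer be amended, the trial report can list patients whose last dose fell 28 days or less before visit 7, with the date to which AEs were actively collected. That would put a number on the gap.

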7. STATISTICAL METHODS AND DETERMINATION OF SAMPLE SIZE

7.1 STATISTICAL DESIGN - MODEL

This is a double-blind, randomized, parallel-group study stratified by presence of any echocardiographic signs indicative of right heart dysfunction to evaluate the efficacy and safety of nintedanib when co-administered with sildenafil, compared to treatment with nintedanib alone, in patients with idiopathic pulmonary fibrosis (IPF) and advanced lung function impairment.

The primary endpoint is the change from baseline in SGRQ total score at week 12.

The primary endpoint will be analysed using a Mixed Effects Model for Repeated Measures (MMRM). The details are provided in [section 7.3.1](#).

The secondary endpoints related to SGRQ and UCSD SOBQ will be analysed using MMRM. Details are provided in [section 7.3.2](#).

The secondary endpoint percentage of patients with on-treatment SAEs from baseline to week 24 will be analysed using the Cochran-Mantel-Haenszel test exploratorily.

Analysis of further endpoints is described in [section 7.3.3](#).

7.2 NULL AND ALTERNATIVE HYPOTHESES

The objective of this study, demonstrating an additional treatment effect of nintedanib co-administered with sildenafil compared to treatment with nintedanib alone, in patients with idiopathic pulmonary fibrosis (IPF) and advanced lung function impairment will be tested using the following null hypothesis:

H_0 : There is no difference in the mean change from baseline in SGRQ total score at week 12 between nintedanib co-administered with sildenafil compared to treatment with nintedanib.

The alternative hypothesis is

H_a : There is a difference in the mean change from baseline in SGRQ total score at week 12 between nintedanib co-administered with sildenafil compared to treatment with nintedanib.

A hierarchical testing procedure will be applied in order to allow for confirmative testing of the secondary endpoints related to SGRQ and UCSD SOBQ also. This procedure is specified in [Table 7.2:1](#).

Table 7.2:1 Flow of hypothesis testing

Step 1	If H_0 is rejected at 5% level (two-sided test) then go to the next step otherwise procedure is stopped and subsequent tests will be done only for exploratory purposes.
Step 2	H_{01} : There is no difference in the mean change from baseline in UCSD SOBQ at week 12 between nintedanib co-administered with sildenafil compared to treatment with nintedanib. H_{a1} : There is a difference in the mean change from baseline in UCSD SOBQ at week 12 between nintedanib co-administered with sildenafil compared to treatment with nintedanib. If H_{01} is rejected at 5% level (two-sided test) then go to the next step otherwise procedure is stopped and subsequent tests will be done only for exploratory purposes.
Step 3	H_{02} : There is no difference in the mean change from baseline in SGRQ total score at week 24 between nintedanib co-administered with sildenafil compared to treatment with nintedanib. H_{a2} : There is a difference in the mean change from baseline in SGRQ total score at week 24 between nintedanib co-administered with sildenafil compared to treatment with nintedanib. If H_{02} is rejected at 5% level (two-sided test) then go to the next step otherwise procedure is stopped and subsequent tests will be done only for exploratory purposes.
Step 4	H_{03} : There is no difference in the mean change from baseline in UCSD SOBQ at week 24 between nintedanib co-administered with sildenafil compared to treatment with nintedanib. H_{a3} : There is a difference in the mean change from baseline in UCSD SOBQ at week 24 between nintedanib co-administered with sildenafil compared to treatment with nintedanib.

The hypotheses will be tested using 5% level of significance (two-sided test). Global type I error will be not exceed 5% within this procedure, thus no adjustment for multiplicity is required.

Statistical tests performed for any other endpoints not included in the above defined testing procedure will also be done only for exploratory purposes.

